Title of the study:

Impact of renal replacement therapy modality on coagulation and platelet function in critically ill patients: Intermittent hemodialysis vs. continuous renal replacement therapy

The National Clinical Trial (NCT) number: NCT04512131

Date of the documenta: December 20, 2023

Study Protocol wih Statistical Analysis Plan (SAP)

Study Protocol

Study design and patients

This was a single-center prospective observational study. The institutional review board at Seoul National University Hospital approved the protocol (H-2007-102-1141). Patients or their surrogates provided written informed consent before enrollment.

Adult patients admitted to a surgical or medical intensive care unit (ICU) and were underwent a session of iHD or at least 48 hours of CRRT or both modalities between August 2020 and January 2023 were included. Patients were excluded if they fulfilled one of the following criteria: duration of CRRT was less than 48 hours, received platelet concentrates, fresh frozen plasma, or cryoprecipitate, discontinuation or initiation of the antiplatelet agents or anticoagulants during the study period, technical errors in laboratory tests.

Renal replacement therapy

All patients underwent either iHD or CRRT or both, according to the clinical situation. The detailed setting of RRT including blood flow rate, dialysis flow rate, ultrafiltration rate, duration, and use of anticoagulants was determined by nephrologists and intensivists. Patients were divided into the iHD or CRRT group according to the applied RRT modality. If both methods were applied to a patient, data from both modalities were included in the analysis. Each patient was exposed to a single episode of iHD or at least 48 hours of continuous venovenous hemodiafiltration or both. In the iHD group, hemodialysis was applied for 2 to 4 hours depending on the clinical condition of patients. Since maintenance iHD is usually performed 3 times a week, 48 hours of CRRT was deemed comparable to a single session of iHD.

Laboratory investigations

In the iHD group, blood samples were obtained immediately before and after the hemodialysis session. In the CRRT group, blood samples were taken within 24 hours of initiation of CRRT and the second samples were taken 48 hours after collection of the first samples.

Rotational thromboelastometry (ROTEM, ROTEM® delta, Pentapharm GmbH, Munich, Germany) was performed to evaluate the impact of RRT on the coagulation system. The Extrinsically Activated ROTEM (EXTEM) assay, which focuses on the extrinsic coagulation pathway and the Fibrin-based EXTEM (FIBTEM) assay, which highlights the fibrinogen function, were performed simultaneously. The clotting time (CT), clot formation time (CFT), α angle, maximum clot firmness (MCF), and maximum lysis measured parameters were recorded for both assays.

The impact on platelet function was assessed by electrical impedance aggregometry

with Multiplate[®] analyzer (Roche, Rotkreuz, Switzerland). To test different pathways of platelet aggregation, aggregation was stimulated 1) by arachidonic acid, the substrate of cyclooxygenase, which subsequently forms the potent platelet activator thromboxane A2 (ASPItest), 2) via adenosine-diphosphate (ADP) receptors by ADP (ADPtest). The area under the curve (AUC) values which is considered the best parameter to reflect overall platelet aggregation of both tests were recorded.

Platelet count and conventional coagulation tests including prothrombin time (PT), activated partial thromboplastin time (aPTT) and fibrinogen assay were performed before and after dialysis. The concentration of D-dimer was measured, which reflects fibrinolysis-specific degradation. The activity levels of protein C and protein S were also measured at two time points. The levels of these vitamin K-dependent anticoagulants were compared between pre- and post-dialysis to evaluate the regulation of clot formation.

Study outcomes

The primary study outcome was changes in CT of EXTEM after dialysis. Secondary outcomes included changes in other EXTEM and FIBTEM parameters, AUC of platelet aggregometry, platelet count, PT, aPTT, fibrinogen concentration, D-dimer concentration, the activity level of protein C and protein S, bleeding events, and transfusion requirements after dialysis. Laboratory test results were compared before and after the application of each dialysis modality. To identify differences in changes according to dialysis modality, a comparison of each study outcome was made between the iHD group and the CRRT group. Bleeding events and transfusion requirements within 24 hours after dialysis in the iHD group or within 24 hours after the second blood sample collection in the CRRT group were also compared between the two groups. The severity of bleeding events were graded

by the modified World Health Organization bleeding scale.

SAP

Based on a previous study regarding the reproducibility of ROTEM results, the mean (\pm standard deviation) CT of EXTEM was set as 55 ± 6.9 seconds before dialysis. An absolute difference of 5 seconds in CT after dialysis was deemed significant. With a two-sided type-I error of 0.05 and a power of 80%, the required sample size was calculated to be 60 patients. Considering a loss to follow-up of 40%, the sample size was increased to 50 patients in each group, resulting in a total sample size of 100 patients.

Normally distributed continuous data were described as means and standard deviation and non-normal distributed data were described as a median and interquartile range [25th–75th interquartile range]. The normality of continuous data was assessed through the Shapiro-Wilk test. Comparisons between groups were performed by using the Student t-test or the Mann-Whitney U test for the continuous variables normally or non-normally distributed, respectively. Categorical variables were reported as numbers and percentages. Categorical data were compared with a chi-square test. A P value less than 0.05 was considered statistically significant and statistical analysis was performed using IBM SPSS 27.0 (IBM Corp, Armonk, NY, USA).

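### Patients are excluded for blood-product use and antithrombotic changes over an undefined window, and the exclusion is not limited to laboratory outcomes, so bleeding and transfusion are compared in groups selected on related events

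*Combined protocol and SAP*

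**What the plan says.** **The exclusion.** Under Study design and patients, patients are excluded if they "received platelet concentrates, fresh frozen plasma, or cryoprecipitate, discontinuation or initiation of the antiplatelet agents or anticoagulants during the study period". The rule acts on the whole patient and names no outcome. Grammatically, the closing time phrase may govern only the drug changes or the blood products as well. The only dated period in the text is the calendar one, August 2020 to January 2023. The same list excludes CRRT lasting under 48 h.

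**The sampling times.** Under Laboratory investigations, iHD "blood samples were obtained immediately before and after the hemodialysis session", and under Renal replacement therapy, "In the iHD group, hemodialysis was applied for 2 to 4 hours depending on the clinical condition of patients". For CRRT, the first "blood samples were taken within 24 hours of initiation of CRRT" and "the second samples were taken 48 hours after collection of the first samples".

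**The clinical comparison.** Under Study outcomes, "Bleeding events and transfusion requirements within 24 hours after dialysis in the iHD group or within 24 hours after the second blood sample collection" (for CRRT) are compared between the groups. The section does not list which blood products count as transfusion.

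**Analysis sets.** The SAP defines no set that brings excluded patients back for bleeding or transfusion and does not provide for reporting exclusions by modality. It allows 40% for loss in both groups without saying whether exclusions count towards it. A patient can contribute to both groups: "If both methods were applied to a patient, data from both modalities were included in the analysis".

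**The concern.** For the laboratory outcomes the exclusion makes sense: a platelet transfusion or a new anticoagulant between two samples would obscure the effect of dialysis on clotting. Bleeding and transfusion are different. Needing platelets or plasma, or having an antithrombotic drug started or stopped, is related to bleeding and to further transfusion. A comparison confined to patients free of those events is a comparison of selected groups.

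Two things could go wrong, depending on the window. If it follows the sampling interval, the selection acts for much longer in CRRT than in iHD. If it reaches into the 24-h outcome window, some patients are removed because they had the outcome. With no window stated and no exclusion counts by modality planned, a reader could not tell which applies or how far the selection shaped the result. Because modality was not randomised, this adds to other non-comparability; it is not the only source.

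**Working it through.** **The plan's own figure.** The plan gives no figure for this exclusion. The nearest is the sample size, which reproduces: n per group = 2 × (1.960 + 0.842)² × 6.9² / 5² = 29.9, so 30 per group and 60 in total; 60 / (1 - 0.40) = 100, or 50 per group. Nothing here disputes it. The 30 per group is used below only for scale.

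**Time in which a patient can be removed, by reading of the window.** Inputs from the protocol: iHD session 2-4 h; CRRT samples 48 h apart; first CRRT sample 0-24 h after start; follow-up 24 h. The look-back lengths are assumptions.

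| Reading | CRRT (h) | iHD (h) | Ratio | Difference (h) |
|---|---|---|---|---|
| First to second sample | 48 | 2-4 | 48/4 = 12 to 48/2 = 24 | 44-46 |
| Start of dialysis to second sample | 48-72 | 2-4 | 48/4 = 12 to 72/2 = 36 | 44-70 |
| First sample to end of follow-up | 72 | 26-28 | 72/28 = 2.6 to 72/26 = 2.8 | 44-46 |
| Look-back of 24 h (assumed) to second sample | 72 | 26-28 | 2.6 to 2.8 | 44-46 |
| Look-back of 72 h (assumed) to second sample | 120 | 74-76 | about 1.6 | 44-46 |
| Calendar period, or no time limit | not computable | not computable | - | - |

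In the third and last rows the 24-h outcome window lies inside the exclusion window. Platelet, plasma or cryoprecipitate transfusion then cannot occur among analysed patients, and only products off the list, such as red cells, could be counted.

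**Illustration for the first row only.** Let d be the 24-h probability of an excluding event, assumed constant and equal in both groups. The proportion removed over T hours is q = 1 - (1 - d)^(T/24).

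- d = 5%: CRRT 1 - 0.95² = 9.75%; iHD 0.43-0.85%; gap 8.90-9.32 points.
- d = 10%: CRRT 1 - 0.90² = 19.00%; iHD 0.87-1.74%; gap 17.26-18.13 points.

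Let D be the 24-h event risk in excluded minus retained patients, assumed equal in both groups. Dropping the excluded patients moves the CRRT-minus-iHD difference by gap × |D|; the direction depends on the sign of D.

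- |D| = 10 points: 0.89-0.93 points (d = 5%) or 1.73-1.81 points (d = 10%).
- D = +50 points: 4.45-4.66 or 8.63-9.06 points.
- D = -20 points: at most 9.32 × 0.20 = 1.9 or 18.13 × 0.20 = 3.6 points. If retained patients have an assumed 20% risk, excluded patients cannot be more than 20 points lower, so this is the limit in that direction.

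For scale, the standard error of a difference at 20% risk with 30 per group is sqrt(2 × 0.2 × 0.8 / 30) = 10.3 points.

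**The case against.** **The outcome window is equal, and 48 h of CRRT is by design the counterpart of one iHD session.** Both are true. They justify the follow-up length and the exposure definition. They do not justify choosing the patients for a clinical outcome by related events beforehand.

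**The 12- to 24-fold contrast depends on one unstated reading.** This stands. A look-back shrinks the ratio, and under the calendar reading no such contrast arises. A reader might take the ratio as established; the documents establish only that the window is undefined. The calendar reading does not rescue the plan, however, because it removes patients for transfusions in the outcome window.

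**The magnitudes are assumed.** This also stands. A constant, equal daily risk is doubtful: anticoagulant use with dialysis is left to clinicians, and if starting it counts as an initiation, exclusions would cluster at the start and not scale with hours. Even the largest illustrated shift, 9.1 points, is below the standard error of 10.3. That weakens the case that the bias is large. It does not remove the bias, which the planned chi-square P value would not reflect.

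**A reader might infer that the filter makes CRRT look safer.** That follows if the excluded patients are those most likely to have the outcome. The documents do not show this: bleeding and red-cell transfusion are not exclusions, and no event rates are given.

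**Comparing patients free of these events is a legitimate, restricted target.** It is, if labelled as such. The plan does not label it.

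**Conclusion.** The concern holds in a limited form. Two secondary between-group comparisons, bleeding and transfusion, are made in patients selected on related events, over a window that the protocol does not define for the individual patient. If the window is first to second sample, it is 48 h against 2-4 h. If it includes the follow-up or the calendar period, part of the transfusion outcome is removed by the exclusion itself, provided that platelets, plasma or cryoprecipitate count as transfusion.

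Neither the size nor the direction of any bias can be established from the documents. The percentages above rest on assumed daily risks and assumed risk differences and are illustration only. A reader might extend the criticism to the primary outcome or to the laboratory use of the exclusion. Neither is supported: the exclusion is defensible there, and the sample size is unaffected. The point deserves a change to the plan, with moderate confidence, but does not undermine the study's main question.

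**What to change.** 1. Report the exclusion window actually applied. Inclusion ended in January 2023 and the document is dated December 2023, so naming a window now could misdescribe what was done. Apply the product and drug-change exclusions to the laboratory analyses only.
2. For bleeding and transfusion, include otherwise eligible, consented patients who met only these exclusions. Keep the existing 24-h window, and show the restricted comparison as a sensitivity analysis. Where a patient contributes to both groups, state to which dialysis episode each exclusion and event belongs.
3. Report exclusion counts and reasons by modality, including CRRT under 48 h. That criterion has no iHD counterpart and remains a selection that this change does not remove.

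**Cost.** SAP wording, a few tables and chart review of excluded patients. The protocol says "Patients or their surrogates provided written informed consent before enrollment", so patients excluded for events after the first sample had probably consented. Whether that consent and the records permit the review is not stated.

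**Downside.** The clinical comparison will then include patients whose later bleeding or transfusion may partly reflect the products or drug changes that they received.

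**If review is not possible.** Report the window, keep the exclusions to the laboratory analyses as far as the data allow, give the counts by modality, and label the bleeding and transfusion comparison as restricted to patients free of these events.

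### Stable antiplatelet users are pooled with non-users in both aggregometry outcomes, so the iHD–CRRT contrast can reflect medication mix if users respond less and their shares differ

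*Combined protocol and SAP*

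**What the plan says.** All references are to the combined protocol and SAP.

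- **Study design and patients:** one exclusion is "discontinuation or initiation of the antiplatelet agents or anticoagulants during the study period". Taking an antiplatelet drug unchanged throughout is not an exclusion.
- **Renal replacement therapy:** modality is not assigned by the study: "All patients underwent either iHD or CRRT or both, according to the clinical situation". A patient who receives both contributes data to both groups.
- **Laboratory investigations:** platelet function is measured by two aggregometry tests with different triggers. One is stimulated "by arachidonic acid, the substrate of cyclooxygenase, which subsequently forms the potent platelet activator thromboxane A2 (ASPItest", the other "via adenosine-diphosphate (ADP) receptors by ADP (ADPtest".
- **Study outcomes:** aggregometry is a secondary outcome: "Secondary outcomes included changes in other EXTEM and FIBTEM parameters, AUC of platelet aggregometry, platelet count" and others. Results are compared before and after each modality, and "a comparison of each study outcome was made between the iHD group and the CRRT group".
- **SAP:** continuous outcomes are compared between groups by Student t-test or Mann-Whitney U test. No stratification, covariate, subgroup or sensitivity analysis is specified for antiplatelet use.

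**The concern.** The exclusion holds drug status constant within a patient, and taking the change from first to second sample removes any constant drug effect on the AUC level. Neither step makes the change itself comparable between users and non-users. If a drug already inhibits the pathway that a test triggers, less aggregation remains for dialysis to remove, and the user's change may be smaller than a non-user's. By general pharmacology this would concern cyclooxygenase inhibitors for ASPItest and P2Y12 inhibitors for ADPtest.

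Two consequences follow, under different conditions. If users respond less, the pooled change understates the change in non-users. If, in addition, the iHD and CRRT groups hold different shares of users, the groups differ in mean change even when the modalities act identically. Because modality follows the clinical situation, nothing in the design equalises those shares. Platelet function is in the study title, and these two AUCs are its only direct functional measures. As planned, a reader could not separate a modality effect from a difference in medication mix.

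**Working it through.** **The plan's own figure.** The only calculation in the SAP concerns EXTEM CT: SD 6.9 s, difference 5 s, two-sided alpha 0.05, power 80%.

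- n per group = 2 × (1.960 + 0.842)² × (6.9/5)² = 2 × 7.85 × 1.904 = 29.9, so 30 per group and 60 in total.
- With 40% loss: 30/(1 − 0.4) = 50 per group, 100 in total.

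This reproduces the stated figures. It does not bear on aggregometry, for which the plan states no effect, SD or sample size.

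**Formula.** Let pI and pC be the user shares in iHD and CRRT, D the mean change in non-users (the same in both groups, so the true modality difference is zero), and fD the mean change in users.

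- Mean change in a group with user share p: D × [1 − p(1 − f)].
- iHD minus CRRT: (1 − f)(pC − pI)D.

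**Assumed inputs.** D = −15 U, f = 0 or 0.5, and every user share are assumptions; the documents give none of them.

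| Users, iHD / CRRT | f | iHD change | CRRT change | Spurious contrast |
|---|---|---|---|---|
| 40% / 10% | 0 | −15 × 0.60 = −9.0 | −15 × 0.90 = −13.5 | 4.5 U |
| 40% / 10% | 0.5 | −15 × 0.80 = −12.0 | −15 × 0.95 = −14.25 | 2.25 U |
| 30% / 20% | 0 | −15 × 0.70 = −10.5 | −15 × 0.80 = −12.0 | 1.5 U |
| 30% / 20% | 0.5 | −15 × 0.85 = −12.75 | −15 × 0.90 = −13.5 | 0.75 U |
| equal shares | any | equal | equal | 0 |
| any | 1 | −15 | −15 | 0 |

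**Dilution alone.** With 30% users in both groups the pooled change is −10.5 U at f = 0 (30% smaller than in non-users) and −12.75 U at f = 0.5 (15% smaller), with no spurious contrast.

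**False-positive rate.** No SD for AUC change is given, so this is in SD units: two independent groups, SD of change within users and within non-users = 1, two-sample t-test at nominal 5%, 10,000 simulated trials per case, no true modality difference.

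| Users, iHD / CRRT | n per group | D | f = 0 | f = 0.5 |
|---|---|---|---|---|
| 30% / 30% | 50 | 1 SD | 5.1% | 5.2% |
| 20% / 40% | 50 | 1 SD | 15.0% | 7.6% |
| 10% / 50% | 50 | 1 SD | 45.2% | 15.8% |
| 20% / 40% | 50 | 0.5 SD | 7.9% | 5.4% |
| 10% / 50% | 50 | 0.5 SD | 16.6% | 7.3% |
| 20% / 40% | 30 | 1 SD | 10.3% | 6.8% |
| 10% / 50% | 30 | 1 SD | 29.2% | 11.7% |

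**Power with equal shares.** At f = 0 a true contrast shrinks to (1 − p) of its size. For illustration I borrow the standardised difference planned for EXTEM CT (5/6.9, about 0.72 SD) and hold the SD fixed. At 30 per group, power falls from 80% with no users to 61% with 20% users and 39% with 40% users. At 50 per group it falls from 95% to 83% and 59%.

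**The case against.** The case on the other side has five parts.

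- **The mechanism is not shown.** A reader might infer that users' AUC sits at the assay's floor and cannot change. The documents do not support that: they report no AUC, assay limit, degree of suppression, drug name or number of users. A low starting value would in any case restrict falls, not rises, and the outcome is defined as a change in either direction. This stands; only possible attenuation can be claimed.
- **One drug need not affect both tests.** A reader might infer that any antiplatelet drug compromises both. The protocol describes two separate pathways, so each test has to be considered against its own drug class. This stands.
- **Bias in the contrast is conditional.** It needs a non-zero dialysis effect, a reduced response in users and unequal shares. The documents show no imbalance, and patients treated with both modalities may reduce it. This stands, but nothing in the plan requires balance or checks for it.
- **Users belong to the study population.** The question concerns critically ill patients, so an average over users and non-users is a legitimate quantity. A reader might conclude that non-users should become the main analysis set; that would change the question, and the documents give no reason to do so. This stands, and it shapes the remedy.
- **The plan already does something.** Excluding starters and stoppers and analysing within-patient change removes constant level differences. That deserves credit, but it leaves a difference in response untouched.

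**Conclusion.** The concern holds as a conditional one. Stable users enter both aggregometry comparisons, modality is not randomised, and the planned tests take no account of antiplatelet use. If users respond less, the pooled change is diluted. If their shares also differ between groups, a modality contrast of (1 − f)(pC − pI)D appears with no modality effect behind it: between 0.75 U and 4.5 U in the unequal-share scenarios above at an assumed D of −15 U, and zero with equal shares or full response. Without an SD for AUC change, whether those amounts are material cannot be judged from the documents.

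It does not follow that the aggregometry results are biased, that users' values are floored, or that the study's main conclusion is at risk. The point concerns two secondary outcomes; the primary outcome, change in EXTEM CT, is unaffected.

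**What to change.** Keep the all-patient comparison for both tests and add to the SAP:

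1. A table of antiplatelet use by drug class and modality group.
2. ASPItest change analysed stratified by, or adjusted for, cyclooxygenase-inhibitor use, and ADPtest change likewise for P2Y12-inhibitor use, with users and non-users shown separately.
3. A sensitivity analysis of each test in patients not taking the relevant class.

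Study design and patients puts the end of the inclusion period at January 2023, and the document is dated December 20, 2023. If added now, these analyses should be labelled post hoc.

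The cost is small. No new samples are needed, and applying the existing exclusion already requires knowledge of each patient's antiplatelet exposure; if drug class was not captured, it would have to be taken from the records. The downside is smaller strata and less precision in these two secondary outcomes. All other outcomes keep every patient as planned.

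### Patients treated with both modalities count in both groups, yet the modality comparison uses tests that assume the groups share no patients

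*Combined protocol and SAP*

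**What the plan says.** Overlap is a stated feature of the design. The Renal replacement therapy section says "All patients underwent either iHD or CRRT or both, according to the clinical situation", then "If both methods were applied to a patient, data from both modalities were included in the analysis", and limits exposure as follows: "Each patient was exposed to a single episode of iHD or at least 48 hours of continuous venovenous hemodiafiltration or both". A patient can thus give at most one record to each group, but may give one to both.

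Under Study outcomes there are two kinds of comparison. One is within modality: "Laboratory test results were compared before and after the application of each dialysis modality". The other is between modalities: "a comparison of each study outcome was made between the iHD group and the CRRT group".

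For the second kind the SAP says "Comparisons between groups were performed by using the Student t-test or the Mann-Whitney U test for the continuous variables", the choice depending on normality, and "Categorical data were compared with a chi-square test". It names no paired, mixed-model, GEE, cluster-robust or McNemar-type method, no rule of one record per patient, and no sensitivity analysis. It does not ask for the number of patients treated with both modalities. On size, it says "the sample size was increased to 50 patients in each group, resulting in a total sample size of 100 patients".

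**The concern.** The three named tests take the two samples as independent. Their standard errors, or null distributions, contain no term for the covariance between two records from the same person. Where shared patients have correlated changes, the P value for the modality contrast is wrong. That contrast is the question in the study title, and it covers the primary outcome (change in EXTEM clotting time) and every secondary outcome, including bleeding and transfusion.

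Positive correlation makes the test conservative and wastes the within-patient information. Negative correlation inflates false positives. Because the plan does not call for the overlap to be reported, a reader could not tell which case applies, or whether any does.

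The unit of counting also slips: 50 records in each group amount to 100 patients only if nobody is in both.

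**Working it through.** **Reproducing the plan's sample size.** Inputs from the SAP: SD 6.9 s, difference 5 s, two-sided alpha 0.05, power 80%, loss 40%. For two independent groups:

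n per group = 2 × (1.96 + 0.84)² × 6.9² / 5² = 29.9, so 30 per group and 60 in all; 60 / (1 - 0.40) = 100.

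This matches the stated 60 and 100. The SAP names no formula, but the calculation for two independent groups reproduces its figures.

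**Effect of overlap on the variance.** Let n be the number per group, f the share of each group made up of shared patients, and r the correlation between a shared patient's iHD change and CRRT change. With equal group sizes and equal SDs:

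- true variance of the difference in means = (2 × SD² / n) × (1 - f × r)
- variance used by the independent-samples test = 2 × SD² / n
- true two-sided alpha = 2 × [1 - Φ(1.96 / √(1 - f × r))]

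Neither f nor r is in the documents, so the values below are assumptions. A stable patient effect cancels in a change score, so r near 0 is plausible.

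The simulations use 50 per group and 20,000 runs per row.

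| f | r | 1 - f × r | alpha, formula | alpha, simulated t-test | alpha, simulated patient-clustered |
|---|---|---|---|---|---|
| 0.2 | 0.2 | 0.96 | 0.045 | 0.044 | 0.048 |
| 0.2 | 0.5 | 0.90 | 0.039 | 0.038 | 0.049 |
| 0.5 | 0.2 | 0.90 | 0.039 | 0.039 | 0.049 |
| 0.5 | 0.5 | 0.75 | 0.024 | 0.023 | 0.049 |
| 0.2 | -0.2 | 1.04 | 0.055 | 0.056 | 0.051 |
| 0.5 | -0.2 | 1.10 | 0.062 | 0.063 | 0.050 |

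At f = 0.1 the formula gives 0.044 for r = 0.5 and 0.052 for r = -0.2. The Mann-Whitney test behaves in the same way. With 50 per group and 25 shared, its simulated alpha is 0.024 at r = 0.5 and 0.065 at r = -0.3.

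**Power.** Take 5 s and SD 6.9 s, as the SAP does. (It gives 6.9 s for pre-dialysis clotting time; using it for the change is the plan's assumption, carried over here.) For f = 0.5 and r = 0.5, with 30 per group, the standardised difference is 5 / (6.9 × √(2/30)) = 2.81.

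- Independent-samples test: Φ((2.81 - 1.96) / √0.75) = 0.84.
- Analysis that allows for the overlap: Φ(2.81 / √0.75 - 1.96) = 0.90.
- With 50 per group the same formulas give 0.97 and 0.99.

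So under positive correlation planned power is not lost; available power is left unused.

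**Number of patients.** Unique patients = 2n - f × n. At 50 per group, f = 0.2 gives 100 - 10 = 90 patients, of whom 10 (11%) had both modalities. f = 0.5 gives 100 - 25 = 75, of whom 25 (33%) had both.

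**The case against.** The harm is conditional and may be small. It needs both overlap and correlation, and change scores give a reason to expect weak correlation. The figure of 0.024 needs a third of all patients to have had both modalities together with r = 0.5. Positive correlation errs on the safe side, and no mechanism for negative correlation is apparent. All of this stands, and it is why the point is not rated more severely.

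The figures also assume equal SDs, which is doubtful when one change spans a 2 to 4 hour session and the other spans 48 hours. If one SD is k times the other, the factor becomes 1 - 2frk/(1 + k²), which lies closer to 1. For k = 2, 0.039 becomes 0.041 (f = 0.2, r = 0.5), 0.024 becomes 0.028 (f = 0.5, r = 0.5), and 0.062 becomes 0.059 (f = 0.5, r = -0.2). For k = 3 they become 0.043, 0.034 and 0.057. With equal group sizes, the tabulated alphas therefore show the largest distortion for a given f and r. The direction is unchanged.

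The within-modality comparisons are listed first under Study outcomes and escape the problem. That limits the scope, but the modality contrast is still a stated comparison for every outcome.

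Finally, inclusion ended in January 2023 and the document is dated December 2023, so a change now would be post hoc. That affects how a reanalysis should be labelled; it does not make the named tests valid for overlapping groups.

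**Conclusion.** The concern holds as a should-fix point. The plan places a dual-modality patient in both groups and then applies tests that require separate groups. That mismatch is certain from the text.

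Its numerical effect is not known, because the documents give neither the overlap nor the correlation. It is nil if either is zero and slight at 10% overlap. Over the tabulated range it reaches at most about half the nominal alpha on the conservative side (0.024) and 0.062 on the other, assuming equal group sizes and equal SDs. It touches only the between-modality comparisons, for the primary and the secondary outcomes.

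**What to change.** - **Report the overlap.** Give the number of unique patients, the number of modality episodes, and the number of patients with both modalities.
- **Continuous outcomes.** Regress the change on modality with patient-clustered standard errors (GEE), or use a patient-level bootstrap. Both handle either sign of correlation. For skewed outcomes, where the plan would use Mann-Whitney, the bootstrap can be applied to a median or rank-based contrast, so the target need not switch to a mean. A mixed model with unstructured within-patient covariance is an alternative. A random intercept alone is not enough, because it cannot represent negative correlation.
- **Bleeding and transfusion.** Use logistic regression with patient clustering or GEE in place of chi-square. The simulations above did not cover binary outcomes, and these models can be unstable if events are few; a patient-level bootstrap of the risk difference is then an option.
- **Sensitivity analysis.** Repeat the comparison using each patient's first modality only. This needs the order of treatment, which the documents do not mention but which sampling dates should supply.
- **Labelling.** State that the analysis was added after enrolment ended, and show the originally named tests beside it.

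The cost is revised SAP wording and a modest reanalysis. No new patients or data are needed.
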